2.11.1.2 Patient ADA status

Any IG sample collected after 150 days of the last dose of LAG525 and/or PDR001 will not be used for summaries or derivations and will only be included in the listing.

Patient ADA status is defined as follows:

- Treatment-induced ADA-positive patient: patient with ADA-negative sample at baseline and at least one treatment-induced ADA-positive sample.
- Treatment-boosted ADA-positive patient: patient with ADA-positive sample at baseline and at least one treatment-boosted ADA-positive sample.
- Treatment-unaffected ADA-positive patient: patient with ADA-positive sample at baseline, no treatment-boosted ADA-positive samples, and at least one treatment-unaffected ADA-positive sample.
- Treatment-reduced ADA-positive patient: patient with ADA-positive sample at baseline and at least one post baseline determinant sample, all of which are ADA-negative samples.
- ADA-negative patient: patient with ADA-negative sample at baseline and at least one post baseline determinant sample, all of which are ADA-negative samples.

- Inconclusive patient: patient who does not qualify as treatment-induced ADA-positive, treatment-boosted ADA-positive, treatment-unaffected ADA-positive, treatment-reduced ADA-positive, or ADA-negative.

The following summaries of ADA patient status (n and %) will be provided using Immunogenicity incidence set:

- Treatment-boosted ADA-positive patients; denominator is the number of patients with ADA-positive sample at baseline.
- Treatment-induced ADA-positive patients; denominator is the number of patients with ADA-negative or ADA- inconclusive sample at baseline.
- ADA-inconclusive subjects: denominator is the number of subjects in Immunogenicity incidence set.
- ADA-negative patients: denominator is the number of patients in Immunogenicity incidence set.
- ADA-positive patients (i.e. ADA incidence): calculated as the number of treatment-boosted ADA-positive and treatment-induced ADA-positive patients; denominator is the number of patients in Immunogenicity incidence set.

Listings will be provided of patient ADA status.

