Amendment 1	07Jul2019	
1. Added list of abbreviations and glossary terms.2. Updated study design adding TNBC and Mesothelioma indications.3. Removed single agent groups from Phase II part.4. Updated the definition of DDS by adding specific wording for different dosing regimens.5. Added the definitions for immunogenicity analysis sets.6. Updated medical history section by adding more details on the analysis.7. Added a subsection on analysis set exclusion.8. Updated the definitions of last date of exposure for both monotherapy and combo therapy.9. Updated definitions of duration of exposure and actual cumulative dose.10. Removed the definitions of cumulative planned doses, percentage of days dosed and percentage of days at planned dose.11. Removed the language about the primary bayesian analysis of ORR for single agent LAG525.12. Added definitions of efficacy endpoints like BOR, ORR, DOR, PFS and TTR.13. Updated language on the efficacy analysis will be done for all patients. Added language about efficacy analysis for patients who switched from single agent to combination.14. Added language on safety summaries and patients who switched from single agent and combination.15. Added language on data analysis for safety and laboratory data.16. Clarified notable high or low values for vital signs.17. Updated language about PK parameters and the PK analysis.18. Added immunogenicity analysis section.19. Added details about calculation of baseline in the appendix.20. Added imputation rules in the appendix.21. Added definitions and derivation rules for irRC in the appendix.22. Removed languages on the construction of waterfall plots and cycle definition.23. Updated the references.
Amendment 2	15Jul2019	Updated language for baseline calculations for efficacy assessments.
Amendment 3	29Oct2020	Clarified PPS
Amendment 4	21Jan2021	Section 2.11.1.1 – Removed from the definition of determinant samples the exclusion for the ADA-inconclusive sample Section 2.8.2.2 - Added information regarding lab conversion units for T4 and regarding the imputed units for the normal ranges.
Amendment 5	15Mar2021	Section 2.8.2.3 – Removed Listing of all clinically relevant laboratory data with values flagged; added tables for worst post-baseline

Version	Date	Changes
		hematology and biochemistry abnormalities based on CTC grades; removed from Table 2-4 'total protein'

List of abbreviations

AE	Adverse Event

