The Immunogenicity prevalence set includes all patients in the Full analysis set with a determinant baseline IG sample **or** at least one determinant post-baseline IG sample.

The Immunogenicity incidence set includes all patients in the Immunogenicity prevalence set with a determinant baseline IG sample **and** at least one determinant post-baseline IG sample.

The IG analysis sets will be different for LAG525 and PDR001.

See [Section 2.11.1.1](#) for the definition of determinant.

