2.11 PD and PK/PD analysis

2.11.1 Immunogenicity

2.11.1.1 Sample ADA Status

Each IG sample is assessed in a three tiered anti-drug anti-body (ADA) testing approach. All IG samples are analyzed in the initial screening assay (first tier). Samples testing negative in the screening assay are not subject to a confirmatory assay. Samples testing positive in the screening assay are then subjected to the confirmatory assay to demonstrate that ADA are specific for the therapeutic protein product (second tier). The titer of confirmatory positive samples will be subsequently determined in the titration assay (third tier). Samples identified as positive in the confirmatory assay are considered ADA positive. Samples can test negative in either the screening or confirmatory assay but for analysis purposes they are not differentiated. The following properties of each sample will be provided in the source data:

- Result of assay according to pre-specified confirmatory cut point: ADA positive (yes) or ADA negative (no)
- Titer (for positive samples): numerical representation of the magnitude of ADA response
- Drug tolerance level: highest drug concentration that does not interfere in the ADA detection method
- Fold titer change (i.e. x-fold): threshold for determining treatment boosted

Determinant samples are defined as samples which are not unevaluable (where unevaluable = sample where assay is not available).

The following definitions apply only to determinant samples:

- ADA-negative sample: Determinant sample where assay is ADA negative and LAG525 (PDR001) PK concentration at the time of IG sample collection is less than the drug tolerance level.

- ADA-positive sample: Determinant sample where assay is ADA positive.
- ADA-inconclusive sample: Sample where assay is ADA negative and LAG525 (PDR001) PK concentration at the time of IG sample collection is greater than or equal to the drug tolerance level or missing.

The following definitions apply only to post-baseline ADA-positive samples with a corresponding determinant baseline sample. To be classified as treatment-boosted or treatment-unaffected, both the post-baseline and baseline titer must be non-missing:

- treatment-induced ADA-positive sample: ADA-positive sample post-baseline with ADA-negative sample at baseline.
- treatment-boosted ADA-positive sample: ADA-positive sample post-baseline with titer that is at least the fold titer change greater than the ADA-positive baseline titer.

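### The treatment-induced ADA rate counts patients with an inconclusive baseline in its denominator although they cannot enter its numerator; the rate is understated by their share, which is probably small

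*SAP*

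**What the plan says.** SAP section 2.11.1.1 sorts samples with an available assay result into three classes. ADA-positive means the assay is positive. ADA-negative means the assay is negative and the drug concentration is below the tolerance level. ADA-inconclusive means the assay is negative but the concentration "is greater than or equal to the drug tolerance level or missing".

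A treatment-induced sample is an "ADA-positive sample post-baseline with ADA-negative sample at baseline". At patient level, section 2.11.1.2 defines treatment-induced as a "patient with ADA-negative sample at baseline and at least one treatment-induced ADA-positive sample". For the corresponding percentage, the "denominator is the number of patients with ADA-negative or ADA- inconclusive sample at baseline".

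Inconclusive samples count as determinant under the current text: "Determinant samples are defined as samples which are not unevaluable", and unevaluable means only that no assay result exists. The document history for Amendment 4 records the change: "Removed from the definition of determinant samples the exclusion for the ADA-inconclusive sample". The incidence set in section 2.2 "includes all patients in the Immunogenicity prevalence set with a determinant baseline IG sample" and at least one determinant post-baseline sample, so a patient whose baseline is inconclusive qualifies.

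Overall ADA incidence adds treatment-induced and treatment-boosted patients and divides by the whole incidence set.

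**The concern.** A proportion should be taken over the patients who could have been counted as cases. The SAP does this for the treatment-boosted rate, which is divided by patients with an ADA-positive baseline. The next line, for treatment-induced ADA, does not: its denominator contains a group that the numerator's definition excludes.

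Emergence of antibodies against LAG525 and PDR001 is a named secondary objective (Protocol Table 3-1; SAP section 1.2). For the treatment-induced rate the mismatch can act in one direction only, making each antibody look less immunogenic than the SAP's own case definition implies. The SAP gives no reason for the wider denominator and plans no analysis with a matched one.

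**Working it through.** The documents state no expected ADA rate and no sample size for immunogenicity, so there is no planned figure to reproduce. The check traces the definitions and then works through the proportions.

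**Where an inconclusive-baseline patient goes.** Take a patient with an inconclusive baseline and a positive sample later.

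- Treatment-induced and ADA-negative status both need an ADA-negative baseline.
- Treatment-boosted, treatment-unaffected and treatment-reduced status all need an ADA-positive baseline.
- Only the residual class is left: "Inconclusive patient: patient who does not qualify as treatment-induced ADA-positive" or for any of the other named statuses.

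The patient is in the denominator of the treatment-induced rate and can never be in its numerator.

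**Formulae.** Let n_neg and n_inc be the numbers of incidence-set patients with ADA-negative and ADA-inconclusive baselines. Let x be the treatment-induced patients, y the inconclusive-baseline patients with a later positive sample, and f = n_inc / (n_neg + n_inc).

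- SAP rate: x / (n_neg + n_inc)
- Matched denominator (A): x / n_neg
- Matched numerator (B): (x + y) / (n_neg + n_inc)

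The SAP rate divided by A is n_neg / (n_neg + n_inc) = 1 - f. The SAP rate cannot exceed A, because its denominator is at least as large, or B, because x ≤ x + y. It is strictly below A as soon as there is one case and one inconclusive baseline.

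**Numbers.** f is not in the documents, so a range is assumed, with an assumed rate of 10% among ADA-negative baselines:

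| f | SAP rate | A |
|---|---|---|
| 0% | 10.0% | 10.0% |
| 5% | 9.5% | 10.0% |
| 10% | 9.0% | 10.0% |
| 20% | 8.0% | 10.0% |
| 30% | 7.0% | 10.0% |

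B also gives 10.0% in every row if inconclusive-baseline patients turn positive at the same rate. In counts: with 180 negative baselines, 20 inconclusive baselines and 18 induced cases, the SAP reports 18/200 = 9.0%. A gives 18/180 = 10.0%. B with y = 2 gives 20/200 = 10.0%.

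**Overall incidence.** Assume 200 patients with 10 positive, 170 negative and 20 inconclusive baselines, 17 induced cases and 1 boosted case. The SAP incidence is 18/200 = 9.0%. Leaving out only the 20 inconclusive baselines gives 18/180 = 10.0%. The dilution again equals the inconclusive-baseline share, here 20/200 = 10%.

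**The case against.** The strongest reply is that f should be close to zero. The first immunogenicity sample is scheduled before the first infusion (Protocol Table 7-6), and this is the first-in-human study of LAG525 (Protocol section 1.2.1.2), so drug at or above tolerance is not expected at baseline. That leaves a missing concentration. But one blood sample serves both PK and immunogenicity (Protocol section 7.2.3.2), values below quantification are set to zero (SAP section 2.9), and concentrations flagged for exclusion are still used for this classification (SAP section 2.11.1.1). An inconclusive baseline therefore mainly requires a lost PK result from a draw whose ADA assay worked. This stands. It limits the size of the error, but it does not make the rule coherent.

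The SAP also tabulates inconclusive patients and lists individual ADA status. That is partial disclosure only. The planned count mixes baseline and post-baseline causes, so the matched rate cannot be read from the table.

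An inconclusive baseline is, after all, assay-negative, so the denominator might be what was intended and the numerator too narrow. That is a fair alternative, and the fix carries it as a sensitivity analysis.

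A reader might go further and infer that overall incidence is badly understated because on-treatment troughs above tolerance make many patients inconclusive. The documents do not support this. Any assay-positive sample is ADA-positive whatever the drug level, so a patient with a negative baseline and high troughs can still become a case and belongs in the denominator. Nor is a rate among patients of conclusive status a correction. ADA-negative patient status requires every post-baseline determinant sample to be negative, so restricting to conclusive patients keeps every detected induced or boosted case and drops only patients who are not cases. Suppose 8 of 100 patients are positive and 40 of the other 92 have an inconclusive post-baseline sample. The restricted rate is 8/60 = 13.3%, even if nothing was masked and the true rate is 8%. Masking may hide some cases, but this figure does not estimate how many.

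**Conclusion.** The treatment-induced rate is wrong as written. Its numerator and denominator describe different patients, and the reported percentage equals the matched rate times (1 - f). The direction is certain; the size is not. It is zero if no baseline is inconclusive, half a percentage point on an assumed 10% at f = 5%, and one point at f = 10%. The larger values of f in the table show the arithmetic and are not a forecast, since nothing in the documents points to so many inconclusive baselines.

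Overall incidence is affected only through the same inconclusive-baseline patients, and only slightly if they are few. Patients who are inconclusive solely because of post-baseline drug levels are properly counted there.

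The impact is low. The summary is descriptive, and no test, success criterion or dose decision in the documents uses it. The reason to correct it is that it reports a named secondary objective and the correction is trivial.

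**What to change.** In SAP section 2.11.1.2:

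1. Make the denominator of the treatment-induced percentage the incidence-set patients with an ADA-negative baseline.
2. Beside that rate, report the number of patients with an inconclusive baseline and how many of them later had a positive sample, separately for LAG525 and PDR001.
3. As a sensitivity analysis, count inconclusive-baseline patients with a post-baseline positive sample as induced and keep the current denominator. Its footnote should say that an antibody present before treatment cannot be ruled out in these patients.
4. Leave overall incidence on the full incidence set. The counts in item 2 let the reader judge the dilution. Do not present a rate restricted to patients of conclusive status as the corrected incidence.

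The cost is a short wording change, one altered denominator, one extra line and one sensitivity row in an existing table. The sample classifications are already derived, and no new data are needed.

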2.12 Interim analyses

No formal interim analyses are planned.

However, in phase I, the dose-escalation design foresees that decisions based on the current data are taken before the end of the study. More precisely, after each cohort in the dose escalation part, the next dose will be chosen depending on the observed data (based on safety, tolerability, PK, [REDACTED] and efficacy data, guided by the recommendations from the BLRM of DLT using EWOC, and recommendations from participating investigators). Details of this procedure and the process for communication with Investigators are provided in [Section 6.2.3](#) of the study protocol.

Data from patients in the phase II part will be reviewed on an ongoing basis to monitor the safety and tolerability of the RP2D in that part of the study. The sample size in any of the 10 groups (6 to 10 and 12 to 16) may be extended to approximately 40 patients, if at least 3 patients have a response (PR or CR) per RECIST 1.1 or irRC for NSCLC, melanoma, renal cancer and mesothelioma, and if at least 2 patients have a response (PR or CR) per RECIST 1.1 or irRC for TNBC. The Investigators and Novartis study personnel will make the decision based on a synthesis of all relevant data available including safety, PK and PD information.

3 Sample size calculation

Please refer to [Section 10.8](#) in the study protocol of LAG525X2101C study ([\[CLAG525X2101C Amendment 10 Section 10.8\]](#)).

4 Appendix

4.1 Baseline

Baseline is the result of an investigation describing the “true” state of the subject before start of study treatment administration.

Baseline (e.g. for laboratory parameters) is considered as the last non-missing assessment or value before start of the first treatment, unless otherwise stated under the related assessment.

For efficacy assessments/events, baseline is the last available and valid assessment performed or value measured within 28 days before the first treatment administration. If pre-treatment administration is not available, assessment within 7 days after first treatment administration can also be considered as baseline assessment.

Baseline could be within 28 days before first treatment administration or on the same day as first treatment administration if specified pre-dose (e.g., ECG). The baseline for measurements of height could be taken any day before first treatment.

If time is recorded for the first treatment dose and for a specific assessment performed the day of first dose, this assessment is considered as baseline only if it is actually performed before the first dose, as checked using both times.

If time is not recorded, a specific assessment performed the day of first dose administration is considered as baseline if, according to protocol, it should be performed before the first dose.

In rare cases where multiple measurements meet the baseline definition, with no further flag or label that can identify the chronological order, then the following rule should be applied: If values are from central and local laboratories, the value from central assessment should be considered as baseline. If multiple values are from the same laboratory (local or central) or collected for ECGs or vital signs, then the last value should be considered as baseline.

Patients with no data on a particular parameter before the first treatment administration will have a missing baseline for this parameter.

For ECG evaluations three serial 12-lead ECGs will be obtained on Cycle 1 Day 1 for each patient, prior to the first administration of study treatment (C1D1). In case the assessments prior to the first administration (C1D1) are missing, the evaluations done at screening will be used for baseline calculations. The average of the ECG measurements at nominal timepoint will serve as the patient’s baseline value for post-dose comparisons.

4.2 Imputation rules

4.2.1 AE, ConMeds and safety assessment date imputation

Table 4-1 Imputation of start dates (AE, CM)

Missing Element	Rule
day, month, and year	
 No imputation will be done for completely missing dates
day, month	
 If available year = year of study treatment start date then 
 If stop date contains a full date and stop date is earlier than study treatment start date then set start date = 01JanYYYY Else set start date = study treatment start date. If available year > year of study treatment start date then 01JanYYYY If available year < year of study treatment start date then 01JulYYYY
day	
 If available month and year = month and year of study treatment start date then 
 If stop date contains a full date and stop date is earlier than study treatment start date then set start date= 01MONYYYYY. Else set start date = study treatment start date. If available month and year > month and year of study treatment start date then 01MONYYYYY If available month and year < month year of study treatment start date then 15MONYYYYY

Any AEs and CMs with partial/missing dates will be displayed as such in the data listings. Any AEs and CMs which are continuing as per data cut-off will be shown as 'ongoing' rather than the end date provided. No imputation will be performed for AEs and CMs end dates.

4.2.2 Other imputations

Incomplete date of initial diagnosis of cancer and date of most recent/first recurrence

Missing day is defaulted to the 15th of the month and missing month and day is defaulted to 01-Jan.

Incomplete assessment dates for tumor assessment

All investigation dates (e.g. MRI scan, CT scan) must be completed with day, month and year. If one or more assessment dates are incomplete but other investigation dates are available, and if the overall response at that assessment is CR/PR/SD/UNK, this/these incomplete date(s) are not considered for calculation of the assessment date and assessment date is calculated as the latest of all investigation dates (e.g. MRI scan, CT scan). Otherwise – if overall response is progression – the assessment date is calculated as the earliest date of all investigation dates at that evaluation number. If all measurement dates have no day recorded, the 1st of the month is used. If the month is not completed, for any of the investigations, the respective assessment will be considered to be at the date which is exactly between previous and following assessment. If

previous and following assessment are not available, this assessment will not be used for any calculation.

Applying the cut-off to tumor assessment

For tumor related assessments, if an evaluation has some assessments done prior to cut-off date and others after the cut-off date, then the evaluation is considered post-cut-off date and will be excluded from analysis.

New anti-neoplastic therapy

Start date:

- If Day is missing, then impute to the max (treatment start date, first day of the month).
- If Day and month are missing then impute to the max (treatment start date, Jan 1).
- If Year, Month and Day are missing then impute to treatment start date.

End date:

No imputation.

Prior anti-neoplastic therapy

Start date:

The same rule which is applied to the imputation of AE/concomitant medication start date will be used, except that 'study treatment start date-1' should be used other than 'study treatment start date' when applicable in the imputation.

End date:

Imputed date = min (start date of study treatment, last day of the month), if day is missing;

Imputed date = min (start date of study treatment, 31DEC), if month and day are missing.

If the end date is not missing and the imputed start date is after the end date, use the end date as the imputed start date.

If both the start date and the end date are imputed and if the imputed start date is after the imputed end date, use the imputed end date as the imputation for the start date.

Missing death date

For cases when either day is missing or both month and day are missing for the date of death, the following imputation rules will be implemented:

- If only day is missing, then impute max [(1 mmm-yyyy), min (last contact date + 1, cut-off date)].
- If both day and month are missing, then impute max [(1 Jan-yyyy, min (last contact date + 1, cut-off date)].

